## 2.2 Preliminary data

[name] primary mentor, [name], performed a large, phase II multisite study evaluating the effects of fish oil vs. soybean oil supplementation on cancer-related fatigue in breast cancer survivors. Compliance with the intervention was excellent, with 84.5% of all participants taking at least 90% of their supplements. Based on the literature, the hypothesis was that fish oil supplementation would alleviate fatigue more than soybean oil due to its high omega-3 fatty acid content and the observation that omega-3 fatty acids can alleviate fatigue. However, soybean oil, despite containing no marine omega-3 fatty acids, has been shown to have antioxidant and anti-inflammatory properties. In [name] study, all participants experienced reduction of fatigue over the course of the 6-week intervention, and those in the soybean oil group had a greater reduction. These data demonstrate that dietary changes may have an impact on symptoms in cancer survivors including cancer-related fatigue.

As part of the study herein, we will collect blood samples to quantify mitochondrial function in circulating T cells and blood-based metabolic biomarkers. [name], the study chair, has developed a protocol to collect blood samples, isolate T cells, and measure real-time respiration in these cells.

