### **4. Study design**

#### *4.1 Brief description and specific aims*

This will be a feasibility pilot randomized controlled trial performed at a single site. We will recruit 42 patients with cancer who are beginning a chemotherapy regimen and randomize them 2:1 to the intervention group or usual care (28 in the intervention arm and 14 in the usual care arm). The uneven allocation serves to improve recruitment, as some patients are disappointed to be assigned to the usual care arm, and allows us to get more information about the intervention. This will be an open label study (due to the nature of the intervention it is not possible to blind participants, and due to the active involvement of the PI in data acquisition, it is not feasible to blind the PI). At baseline, participants will complete an on-study form that includes demographics and clinical characteristics. They will complete a 3-day food record (ideally from two weekdays and one weekend day), a fasted blood draw, and several questionnaires [i.e., 14-Item Mediterranean Diet Assessment Tool, Functional Assessment of Chronic Illness Therapy – Fatigue (FACIT-F), Aerobics Center Longitudinal Study (ACLS) physical activity questionnaire, Brief Fatigue Inventory (BFI), 27-item Symptom Inventory, Functional Assessment of Cancer Therapy-Cognition (FACT-Cog), Brief Pain Inventory (BPI), Insomnia Severity Index (ISI)]. For the duration of the study, all participants will complete a daily diary that includes their average fatigue level that day. For 4 weeks, we will provide participants in the intervention group with food based on the Mediterranean Diet. We intend this food to be substituted or supplemented with other food of the patients' choosing, though we encourage participants to comply with the Mediterranean Diet for all meals and snacks. During this time we will also provide education regarding the principles and composition of the Mediterranean Diet and how to effectively implement it at home. This education will include materials that encourage behavior change to inspire motivation and adherence to the diet. At 4 weeks, participants will undergo a mid-point evaluation where they will complete the same assessments as at baseline except for the on-study form. For weeks 5-8, participants in the intervention group will be encouraged to follow the Mediterranean Diet though we will not provide food. During the 8-week intervention, we will be in contact with participants in both groups to monitor adverse events and discuss any barriers to consuming the diet (in the intervention group). At 8 weeks, participants will repeat the assessments and undergo an exit interview, which will last approximately 15-30 min. Participants will receive \$20 total to complete baseline and post-intervention measures and those in the intervention group will receive free meals for 4 weeks. Those in the usual care group will be offered the intervention materials and one week of meals *gratis* at the conclusion of the study.

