Either [name] (study chair) or a member of the study staff who was trained by [name] will deliver the intervention. The intervention will be standardized and include a checklist for the interventionist to ensure fidelity of the intervention and to prevent drift. For interventions delivered by a staff member other than [name], at least one out of five sessions will be either attended by [name] or audio-recorded; feedback will be provided to the interventionist.

We will contact participants once a week so that we can check in, assess adverse events, and troubleshoot any issues with compliance.

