#### *4.4.3 Mechanistic aims: Metabolic measures*

Blood will be collected at the Wilmot Cancer Institute, Pluta Cancer Center, a UR Lab Patient Service Center, or medical office and a trained study staff member will transport the samples to our facility. Participants will be requested to fast overnight (at least 8 hours) before the blood draw. The location will be selected to minimize subject burden and if possible we will perform blood draws at the same time as a regularly scheduled medical blood draws. If a participant is not fasted at the time of the blood draw, blood will still be drawn and a note will be made. The blood draw can occur the same day as their chemotherapy infusion, or at another time.

Approximately 40 mL of blood (around 3 tablespoons) will be drawn at baseline (week 0); approximately 40 mL will be drawn at 4 weeks, and approximately 20 mL of blood will be drawn at 8 weeks. This is a total of approximately 100 mL of blood over 9 weeks. We will collect the following:

1. At baseline and 4 weeks, we will collect blood in two light-green-top (sodium heparin) tubes (10 mL each, 20 mL total). These tubes will be inverted 8-10 times and stored at room temperature. They will be used the same day for T cell extraction and real-time metabolic assays for basal respiration, maximal oxygen consumption, etc.
2. At baseline, 4 weeks, and 8 weeks, we will collect blood in two tubes (red top and/or serum separator); these will be sent to UR Labs for analysis and/or brought to the CCPL.

Live-cell metabolic assays will be conducted by [name] or trained study staff. First, T cells will be isolated using established procedures, and plated on a Seahorse 48-well plate. The Extracellular Flux XF instrument (also known as the Seahorse) in the Flow Cytometry Core will be used to perform a standard Mitochondrial Stress Test. This test involves injecting metabolic inhibitors onto the cells *ex vivo* to evaluate oxygen consumption rate and extracellular acidification rate (ECAR, i.e., change in pH), which provides detailed information regarding mitochondrial function. Other metabolic measures will be assessed either by UR Labs or in the CCPL.

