#### *8.2.5 Randomization procedures*

Randomization will be revealed to the participant at the end of the baseline assessments, before delivering the instructional portion of the intervention.

We will employ two treatment arms in a 2:1 allocation ratio:

1. Mediterranean Diet: an 8-week intervention entailing education of the Mediterranean Diet and delivery of Mediterranean Diet-inspired meals for 4 weeks.
2. Usual care: completion of assessments, with no intervention and usual care for their cancer.

Consented subjects will be randomized with a computer-generated random numbers table with block sizes of 3 and 6 and stratified based on how frequently they will be receiving chemotherapy (weekly, biweekly, or every 4 weeks vs. other). The random numbers tables will be generated centrally by [name], the project biostatistician, or a designee. A total enrollment of 42 subjects is planned.

Participants cannot be blinded due to the nature of the intervention. PI blinding is also not feasible given that the PI will play an active role in recruitment, intervention delivery, data acquisition, and analysis.

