##### *14.2 Study teams' access to participant information*

eRecord will be used to help screen patients and extract data. Only those with proper training will have access to this database and medical records.

Some study data will be collected electronically using REDCap software, and any eConsents will be conducted using REDCap. REDCap is a secure, web-based application for building and managing online surveys and databases and is made available through the CTSI. Study data in REDCap will only be accessed by members of the study team.

All other study data—paper-and-pencil forms, biological samples—will be labeled with Participant ID and participant initials and not identifiable information. Only members of the study team or those analyzing the data/samples will have access to these.

All data will be compiled into several databases that will identify participants by Participant ID and *not* name or contact information. If data are shared in the future with other researchers (e.g., a trainee), only

databases without identifiable information will be shared and access will only be given to that specific individual.

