### *17.2 Data Handling, Rigor, Quality, and Reproducibility:*

Data will be entered in REDCap electronic forms and electronically collated in a HIPAA-compliant REDCap database managed by our Division. After collation, data will be audited electronically and visually, as needed, for errors. Appropriate graphical or statistical diagnostics methods will be employed in each of the analyses to evaluate distribution of variables (e.g., to identify shape of the distribution and outliers) and also to evaluate the model assumptions (e.g., if deviation from the statistical assumptions is found, we will use alternative methods such as transformations or nonparametric analyses). Outliers that are detected will be investigated to determine if they are due to error. If not, analyses will be conducted with and without them to assess sensitivity. Because this is a preliminary efficacy study, unless stated otherwise, all hypothesis testing will be at the two-sided 0.15 level as appropriate for screening trials. SAS, JMP, and/or R software will be used for the analyses. Following the intent-to-treat principle, all randomized survivors will be analyzed in the arm as allocated, regardless of their compliance with the intervention or Mediterranean Diet contamination in the control group.

Although participants will be randomly assigned, differences may be present between study arms on demographic or clinical variables. Study arms will be compared on baseline demographic (e.g., age), clinical (e.g., cancer diagnosis, type of chemotherapy), and behavioral (e.g., physical activity, smoking) variables. If significant imbalance is found for a variable, it will be included as a covariate in subsequent analyses following standard practice.

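### No step masks the T-cell assay, so a person who delivers the diet may also run the week-4 mitochondrial test and judge its errors knowing the arm

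*Combined protocol and SAP*

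**What the plan says.** The trial is open label. Participants are not blinded because of the nature of the intervention. For the PI, section 4.1 gives one reason: "due to the active involvement of the PI in data acquisition, it is not feasible to blind the PI". Section 8.2.5 gives more: "PI blinding is also not feasible given that the PI will play an active role in recruitment, intervention delivery, data acquisition, and analysis".

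Roles are described in three places:
- Section 4.3.1, on the diet: "Either [name] (study chair) or a member of the study staff who was trained by [name] will deliver the intervention".
- Section 2.2, on the assay method: "the study chair, has developed a protocol to collect blood samples, isolate T cells, and measure real-time respiration in these cells".
- Section 4.4.3, on running the assay: "Live-cell metabolic assays will be conducted by [name] or trained study staff". The tubes are for fresh cells: "They will be used the same day for T cell extraction and real-time metabolic assays".

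Section 14.2 says that paper forms and biological samples "will be labeled with Participant ID and participant initials and not identifiable information". Section 17.2 deals with extreme values: "Outliers that are detected will be investigated to determine if they are due to error". If they are not errors, the analysis is run with and without them.

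Section 4.1 states the week-4 hypothesis with a direction for each T-cell measure: higher ATP turnover, higher spare respiratory capacity and a smaller proton leak in the diet arm. Section 8.2.5 places the reveal of allocation to the participant at the end of the baseline assessments.

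**The concern.** The reason given for not blinding the PI fits recruitment and delivery of the diet. It does not fit the reading of a laboratory plate. Nobody needs to know the arm to run a stress test, process its raw file or decide whether a value is an error. The plan nevertheless has no masked tube or plate code, does not separate delivery from assay work, and does not require that quality decisions precede knowledge of the arm.

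The mechanistic result is at stake. Section 17.4.3 uses the biomarkers to decide which to carry into follow-up studies, and section 4.5 plans a manuscript on the metabolic outcomes. If values were produced or discarded by someone who knew the arm and expected a given direction, a between-arm difference could partly reflect that expectation. Once values have been cleaned with the arm known, masking cannot be restored.

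**Working it through.** **Step 1. Can the same person deliver the diet and handle the week-4 assay knowing the arm?**

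| Question | Where | What it allows |
|---|---|---|
| Who delivers the diet? | 4.3.1 | Study chair, or staff trained for it |
| Who runs the assay? | 4.4.3 | A named person (name removed), or trained study staff |
| Who devised the assay protocol? | 2.2 | Study chair |
| What does the PI do? | 8.2.5 | Recruitment, delivery, data acquisition and analysis |
| How are samples marked? | 14.2 | Participant ID and initials |
| Is the arm known by week 4? | 8.2.5 | Yes, to the participant and to anyone delivering the diet |
| Who judges errors, and is it masked? | 17.2 | Neither is stated |

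So the text permits the overlap without requiring it. ID and initials do not hide the arm from someone in weekly contact with participants (4.3.1), in a study that recruits 2-3 people a month (4.5).

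**Step 2. Does section 17.2 close the gap?** Only in part. The with-and-without analysis applies to outliers that are not judged errors. A value judged an error has no such check, and nothing says that this judgement is made without sight of the arm. The documents do not describe well exclusion or normalisation. I assume that such steps occur when a 48-well plate is processed.

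**Step 3. The plan's own calculation.** Section 17.1 gives 80% power for FACIT-F with n = 33 (22:11), effect size 0.75, correlation 0.50 and a two-sided 0.15 level, by ANCOVA.

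- SE = sqrt(1 − 0.50²) × sqrt(1/22 + 1/11) = 0.866 × 0.369 = 0.320 SD.
- Critical t with 30 df, two-sided 0.15: 1.477.
- Non-centrality: 0.75 / 0.320 = 2.345. Power by non-central t: 80.6%.

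This reproduces the stated 80%. The documents contain no such calculation for the T-cell measures.

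**Step 4. Illustration for one T-cell measure.** Suppose there is no true effect, but handling shifts one arm by b SD in the hypothesised direction. Non-centrality is b / 0.320, and the rejection rate follows from the same non-central t.

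| Assumed shift b (SD) | Non-centrality | False-positive rate |
|---|---|---|
| 0 | 0 | 15.0% |
| 0.1 | 0.313 | 16.9% |
| 0.2 | 0.625 | 22.5% |
| 0.3 | 0.938 | 31.1% |

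**Step 5. Sensitivity to the correlation.** The 0.50 is given only for FACIT-F, so for the assay it is an assumption. With correlations from 0 to 0.8, SE = sqrt(1 − r²) × 0.369 runs from 0.369 to 0.222 SD. The rate for a 0.2 SD shift then runs from 21% to 30%, and for a 0.3 SD shift from 27% to 46%. The 22:11 split is overall retention. Section 13 lets participants skip a blood draw, so fewer assay results may be available.

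**The case against.** The case on the other side is substantial, and most of it stands as a limit on the point.

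- **Blinding is not refused for everyone.** A reader might infer that the protocol rules it out for all roles. It rules it out for participants and the PI, and is silent on laboratory staff.
- **The operator is not identified.** Names are removed from 4.4.3. That the named operator is the study chair is plausible from 2.2, 4.3.1 and 8.2.5 but not established.
- **No contrast between a blind baseline and an unblinded week 4 is shown.** Section 8.2.5 dates the reveal to the participant. It does not say when staff learn the arm. Section 6.1.1 describes a joint baseline and randomization appointment, and blood is assayed later the same day, so a baseline run could also follow the reveal.
- **The assay is not stated to be corroboration of the fatigue result.** A reader might infer this because fatigue is self-reported by unblinded participants. Sections 2.3 and 17.4.3 give other purposes: describing metabolic effects of chemotherapy, drawing associations with symptoms and choosing biomarkers for later work.
- **The aim is preliminary.** Section 17.4.4 says secondary and exploratory analyses will be read very cautiously. The Mechanistic Aim also includes glucose and insulin, and section 4.4.3 assigns the other metabolic measures to UR Labs or the CCPL.
- **Coding the tubes conceals only partly.** With fresh same-day samples and slow accrual, the day of the run can identify the participant.

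These arguments reduce the weight of the point. They do not supply a masking step, and the last does not apply with the same force to processing coded raw files in a later single pass.

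**Conclusion.** The gap is real and modest. The documents permit one person to deliver the diet, run the week-4 stress test and judge which values are errors, with the arm known throughout. The sensitivity analysis in 17.2 does not reach values discarded as errors. Expectation bias could therefore enter a directional mechanistic result. It does not touch the feasibility criteria, and masking the assay would neither help nor harm FACIT-F.

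The size is unknown. The rise from 15% to about 17%, 23% or 31% rests on assumed shifts of 0.1 to 0.3 SD, an assay correlation of 0.50 borrowed from FACIT-F, and 22:11 available assay results. It shows how sensitive a test at the 0.15 level is to small handling shifts. It is not an estimate of bias in this trial, and the documents give no evidence that bias would occur. The change is worth making because it is cheap and cannot be made after the values have been cleaned.

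**What to change.** 1. In 4.1 and 8.2.5, limit the no-blinding statement to participants and intervention delivery. Set out the assay masking in 4.4.3.
2. Store raw plate files under a random code, without participant ID or initials. The code list should be held by someone who does not process the files.
3. Make all well-exclusion, normalisation and error or outlier decisions in one pass, and record them before the code is linked to arm. This step gives the most protection.
4. Where scheduling allows, have the plate run by trained staff, already permitted in 4.4.3, who do not deliver that participant's diet.

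**Cost:** protocol and laboratory-procedure wording, a code list, some scheduling, and slightly later availability of cleaned values. Item 3 needs no extra staff, samples or assays, and sample size and power do not change. Concealment at the bench stays partial because fresh samples arrive a few at a time.

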#### 4.2 Subject population

We will recruit 42 patients with cancer undergoing chemotherapy from Wilmot Cancer Institute or a satellite clinic (e.g., Pluta Cancer Center). In particular, these patients will have a recent diagnosis of cancer (any type except brain cancer), and will represent a broad range of patients seen at Wilmot Cancer Institute including young and old; men and women; those of various ethnic and racial categories (**Table 1**); those who are underweight, normal weight, and overweight; those with and without underlying metabolic dysfunction (e.g., diabetes); and those undergoing various types of chemotherapy treatment.

From previous local studies completed by our group, we expect a 20% withdrawal rate, resulting in approximately 33 participants with evaluable data (approximately 22 in the intervention group and 11 in the usual care group).

No vulnerable classes of subjects such as fetuses, neonates, children, pregnant women, prisoners, institutionalized individuals, or decisionally impaired adults will be recruited.

Total planned enrollment: 42 participants

**Table 1.** Targeted/planned enrollment by ethnic and racial categories:

Ethnic Category	Sex/Gender		
	Females	Males	Total
Hispanic or Latino	2	1	3
Not Hispanic or Latino	26	13	39
Ethnic Category: Total of All Subjects	28	14	42
Racial Categories			
American Indian/Alaska Native	0	0	0
Asian	2	1	3
Native Hawaiian or Other Pacific Islander	0	1	1
Black or African American	3	2	5
White	23	10	33
Racial Categories: Total of All Subjects	28	14	42

We will recruit males and females to this study and expect to recruit more females because a large number of participants will likely be recruited from the breast cancer clinic. Based on the characteristics of samples recruited for recently completed local studies by our group, we anticipate that the potential sample pool for the current study will be mostly White/non-Hispanic individuals, though we will encourage patients of other racial and ethnic groups to participate. The average age for studies conducted by our group tends to be approximately 65 years, though we would like to invite younger patients (e.g., in their 20's and 30's) and much older patients (e.g., in their 80's) to participate in our study as well. Children, individuals under the age of 18, as defined by the NIH Grants Policy Statement, will not be included because their nutritional intake is often determined by their parents/guardians/caregivers and their metabolic function is different than the adult population due to their growth and development during maturation.

#### 4.3 Study interventions

Participants will be randomly assigned 2:1 to a Mediterranean Diet or usual care using a computer-generated random numbers table with blocks of 3 or 6. Patients will be stratified based on how frequently their chemotherapy is planned to be administered. One strata will include patients who plan to receive

[figure not shown]
weekly, biweekly (Q2w), or every 4-week (Q4w) regimens, and the other strata will include those on other regimens (e.g., Q3w). This stratification will allow us to account for who is at the “end” of a cycle and who is in the “middle” of a cycle at the 4- and 8-week assessment points.

#### *4.3.1 Mediterranean Diet intervention*

The first 4 weeks of the intervention we will provide food as well as a Mediterranean cookbook and tips to follow a Mediterranean Diet in the home. The menu will be based on the Mediterranean Diet Pyramid (**Fig. 2**) and the Mediterranean Exchange List developed by Djuric et al. (2008) for implementation in research. These guidelines include categories of foods (e.g., dark green vegetables, high-monounsaturated fatty acids), goal amounts of each category, and foods that fall into each category. Consumption of all of the food provided to the participant will cause them to be adherent with the Mediterranean Diet intervention, and foods can be substituted with the participant still being adherent. Although red wine is recommended as part of the Mediterranean Diet, we will not recommend or provide any alcohol due to lack of research regarding the benefits/drawbacks of alcohol consumption on the efficacy of the chemotherapy or supportive care outcomes. The menu will include meals every day for one week (7 breakfasts, 7 lunches, and 7 dinners) plus snacks, and then the menu will be repeated four times to span the four-week period. The provided food will be approximately 1,600 kcal/day (1,200-2,000 kcal), though participants will be encouraged to consume additional food to avoid hunger. These diets have been developed in conjunction with [name], [name], and their staff at the Highland Hospital’s Weight Management & Lifestyle Center (NCT03045289). Their team has successfully developed and executed a plant-based diet intervention and is developing a Dietary Approaches to Stop Hypertension (DASH) diet intervention (NCT04048642). The Mediterranean Diet menu will be assessed for completeness and safety in conjunction with a registered dietitian (e.g., [name], RD; [name], RD).

The food will be supplied by a combination of Project Lean Nation and a local grocery store/food supplier (e.g., Wegmans). Project Lean Nation meals are high in lean protein and vegetables; they are flash-frozen, which allows the structure and the nutritional contents to be preserved with minimal artificial preservatives. Twelve meals per week will be supplied by Project Lean Nation, and meals will either be provided to the patient at the hospital or delivered to the participants’ homes once per week for 4 weeks. These meals include items such as the Falafel Plate, Spaghetti & Meatballs, and Pan-Roasted Salmon. We will then provide the rest of the food via a local grocery store/food supplier. We will give participants some key ingredients at the beginning of the study and have additional food delivered to their homes weekly via Instacart. This food will include breakfast items (e.g., oatmeal with nuts and dried fruit) as well as other Mediterranean Diet staples (e.g., olive oil, fresh greens, fresh fruit).

The composition of the meals will be based on following guidelines.

© 2010 Fundación Dieta Mediterránea  
The use and promotion of this pyramid is recommended without any restriction

**Fig. 2.** The Mediterranean Diet guidelines.

It is the goal that the meals are appetizing and enjoyable. The meals will include herbs and spices (e.g., oregano, garlic) and will not intentionally be low-salt or low-fat. To reiterate, all participants will be encouraged to supplement the meals with food that conforms to the Mediterranean Diet, especially olive oil, whole grains, fruit, and nuts; to eat as much as they want; and to consume their own meals and snacks in place of the provided meals if they prefer to do so, provided the supplemental food fits within the Mediterranean Diet plan. The provided food is offered primarily to enhance adherence to the diet. The day and the time of each meal will *not* be specified. Some sample menu items could include the following.

Breakfasts (approx. 400 kcal):

- Oatmeal with walnuts and raisins

Lunches or dinners (approx. 500 kcal):

- Pan-roasted salmon
- Spaghetti and meatballs
- Falafel
- Chicken taco

Snacks or side dishes (approx. 100 kcal):

- V8 beverage
- Nuts
- Fruit (fresh, dried, canned, or frozen)
- Whole wheat crackers with hummus

Most of the food will be either frozen or shelf-stable at room temperature and require minimal preparation. Storage and reheating instructions will be provided.

At the beginning of the study, participants in the Mediterranean Diet group will receive a cookbook that includes information about the Mediterranean Diet (e.g., history, purported benefits) as well as recipes and will be encouraged to follow its practices for snacks or any supplementary food. The meals provided in our cookbook are selected to be compliant with the Mediterranean Diet but also require little preparation and no rare ingredients (i.e., all ingredients should be readily available at the local grocery store). It will also include “snacks,” or food that one can have on-hand that require little to no preparation. During week 3 or 4, participants will have an education session to discuss how to effectively implement a Mediterranean Diet into their routine. This session will be loosely based on a combination of behavioral theory and cognitive behavioral theory. Participants will be taught a variety of strategies to promote behavior change, as listed in **Table 2**.

Strategies of behavior change	Action plan to promote adherence
Self-monitoring	Food log
Problem solving	Plan meals and grocery store trips
Goal setting	Definite time frame (4 weeks), weekly goals if applicable
Contingency management	Keep nutrient-dense snacks handy
Cognitive restructuring	Think of food as medicine
Social support	Involve spouse/roommates, especially those with whom participant shares meals
Stimulus control	Make sweets less accessible
Stress management	Positive attitude, acceptance, relaxation
Relapse prevention	Start each day anew; do not consider a day "ruined" if ate non-compliant food

**Table 2.** Strategies of behavior change (left column) with examples of how each could be implemented (right column)

In a standardized educational session, a member of the study staff will discuss each of the strategies, and then select a subset to focus on. In the second half of the intervention, participants will continue to receive a weekly check-in with the study team. As in the first half of the intervention, we will discuss barriers to adhering to the intervention and potential strategies to overcome those barriers.

Either [name] (study chair) or a member of the study staff who was trained by [name] will deliver the intervention. The intervention will be standardized and include a checklist for the interventionist to ensure fidelity of the intervention and to prevent drift. For interventions delivered by a staff member other than [name], at least one out of five sessions will be either attended by [name] or audio-recorded; feedback will be provided to the interventionist.

We will contact participants once a week so that we can check in, assess adverse events, and troubleshoot any issues with compliance.

